### **Cell sorting**

Tissue preparations encompassing the myenteric plexus will be dissociated described and single cell solutions labelled for flow cytometry using standardised methods established within our laboratory on a FACSCanto II flow cytometers within the University of Liverpool Flow cytometry facility. We will quantify cells expressing neuronal, glial and progenitor cell markers, including those assessed by qRT-PCR as well as novel markers determined by scRNA-Seq. Our analysis will provide quantification of numbers of cell types and relative expression levels by signal intensity.

# Stimulation of key signalling pathways in neurospheres

The role of the following key signalling pathways will be assessed for their capacity to modulate progenitor cells within cultured neurospheres:

- a. Notch signalling using chemical inhibition (DAPT) and siRNA knockdown of RBPkJ
- b. Serotonin signalling using pharmacological serotonin receptor agonists and antagonists
- c. Sonic hedgehog signalling pharmacological inhibition of the sonic hedgehog pathway
- d. Pathways identified in the scRNA-Seq analysis will be included in this work stream.

#### **Transplantation of cells**

Cells will be dissociated from neurospheres and then labelled with a fluorescent protein such as GFP using lentiviral transfection to allow the tracking of the migration of these cells and their progeny post transplantation. Following purification (removal of viral particles) a single cell suspension will be produced and microinjected into bowel explants. The transplanted model will then be cultured and assessment of the degree of colonisation made at set time points. This assessment will be made by various microscopy techniques and immunofluorescent analysis as described above. Single cells as well as intact neurospheres may be transplanted to compare the optimal transplantation technique.

## **Linking with clinical outcomes**

Patients recruited for this study who have Hirschsprung's Disease are also eligible for the ALOHA study (REC: 18/NNW/0608) which is being run by the same study team in the same institution. Linkage of the clinical outcomes data with the laboratory-based data described above is expected to shed novel light onto the findings and is an important step towards clinical translation of this work.

# Statistical analysis

All quantitative results will be analysed using appropriate statistical measures. For complex statistics the Biostatistics Department at the University of Liverpool will be consulted.

#### 9. Outcome measures

The milestones for outcome will be:

- 1) Successful optimisation of a scRNAseq protocol using dissociated human bowel cells.
- 2) Identification and description of the populations of progenitor cells which are present within the dissociated cells from different regions of children with HSCR and control patient groups.
- 3) Determination of the mechanisms and signalling pathways responsible for ENSPC proliferation and differentiation in neurospheres.
- 4) Manipulation of neurospheres using targeted agonists and antagonists for key pathways.
- 5) Transplantation of cells into explant tissue ex vivo and characterising of cell integration.

# 9. Study end-point

It is anticipated that achieving these study outcomes including refining protocols and gaining sufficient data within each workstream will require 150 Hirschsprung's specimens and 300 control specimens.

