# 5. Rationale and significance

The current gold-standard treatment for HSCR is to surgically remove the affected bowel to restore normal bowel function and enable passage of stool. However, this often has unsatisfactory outcomes: after surgery ~30% of children have constipation, incontinence or recurrent episodes of enterocolitis and 10% will need a permanent stoma (6). These outcomes are associated with psychological difficulties and significantly impact the quality of life of children and their families. Thus, there is an urgent need to improve the treatment of babies and children with HSCR.

The proposed work is a logical continuation of our previous studies (Research Ethics Committee (04/09/RE "Isolation of Human Enteric Nervous System Stem Cells" and 10/69/RE "Enteric nervous system stem cell behaviour in mature muscle models"). We have previously demonstrated that we can isolate and culture human ENSPCs and that these cells can be transplanted into aganglionic bowel to restore contractility (17). However, there are still outstanding questions on how these cells can be optimised for successful transplantation before this work can be translated to clinical trials:

- 1) What are the characteristics of the ENSPCs that can be transplanted and go on to proliferate and differentiate.
- 2) Safety: Do all these cells differentiate? Are the stem cells adequately controlled within microenvironmental niches that prevent uncontrolled growth?
- 3) What is the ideal method of transplantation? This may be whole neurospheres or single cells, with and without pharmacological agents to aid the differentiation of the ENSPCs.
- 4) Can the progenitor cells be modulated in vivo to avoid transplantation using medication?

This project is designed to begin to answer these questions using established protocols from our lab as well as incorporating new approaches such as single cell transcriptomics. Firstly, we aim to compare the progenitor populations in ganglionic, transition zone and aganglionosis bowel from children with HSCR as well as control ganglionic bowel. We will do this by examining full thickness bowel tissue sections and neurospheres with histology and single cell transcriptomic analysis. While recent publications have used single cell analysis of neuronal and glial cell populations (24, 25), it has not been carried out in progenitor populations or in HSCR samples.

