## Single cell analysis

Following dissociation of tissue to single cells from patient tissue we would prepare for a recovery of 10,000 cells and 20,000 reads per cell. The samples will be run on a NovaSeq 6000 using an S2 flow cell for an estimated output of 3.3 billion reads, at the Centre for Genomic Research (CGR, University of Liverpool). We will use the Chromium X fixed RNA workflow which allows collection and storage of samples, followed by library preparation and sequencing of all collected samples in one day. The single cell whole-transcriptome sequencing data will be analysed using the computing program R and cells will be clustered according to their principle components using cell cluster analysis software/programmes CellRanger and Seurat. Neuronal progenitor cells will be identified and transcription factors will be interrogated for significant differences using Ingenuity Pathway Analysis. Specifically, we will be looking at the molecular profiles of individual cells to discriminate between different types of cells.

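### Can one sequencing run of about 16 samples be squared with 150 Hirschsprung's and 300 control specimens?

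*Protocol*

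**What the plan says.** Section 9, Study end-point, gives the only sample numbers in the protocol. It expects that meeting the study outcomes, including protocol refinement and "gaining sufficient data within each workstream will require 150 Hirschsprung's specimens and 300 control specimens". It does not divide these by workstream or bowel region, and does not say whether a specimen is a whole resection or a sample from one region.

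The Single cell analysis part of section 8 says the team would "prepare for a recovery of 10,000 cells and 20,000 reads per cell". Samples will be "run on a NovaSeq 6000 using an S2 flow cell for an estimated output of 3.3 billion reads". The fixed-RNA workflow lets samples be collected and stored, "followed by library preparation and sequencing of all collected samples in one day". In the progenitor cells, "transcription factors will be interrogated for significant differences using Ingenuity Pathway Analysis".

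Section 5 aims to "compare the progenitor populations in ganglionic, transition zone and aganglionosis bowel from children with HSCR as well as control ganglionic bowel", which makes four tissue types, by "examining full thickness bowel tissue sections and neurospheres with histology and single cell transcriptomic analysis". The second milestone in section 9, Outcome measures, is "Identification and description of the populations of progenitor cells which are present within the dissociated cells from different regions of children with HSCR" and in controls.

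Handling of human tissue samples, also in section 8, states that tissues will not all undergo every investigation and that the selection depends on the question being answered.

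**The concern.** The total is linked to enough data in each workstream, and single-cell sequencing is one of them. A reader could take it that 150 and 300 specimens stand behind the sequencing comparison. The sequencing figures point to a far smaller number, and the text also has all collected samples processed in one day on what reads as one flow cell. Taken literally for every specimen, these statements cannot all be true.

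The sequencing looks for significant differences between tissue types, and its results supply markers for qPCR and cell sorting and pathways for the neurosphere stimulation work. If the comparison rests on a handful of children per tissue type, differences between children could be mistaken for differences between tissues, and the error would pass to later experiments.

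**Working it through.** **Inputs.** Cells 10,000, depth 20,000 reads per cell and output 3.3 billion reads come from Single cell analysis. Specimens 150 + 300 = 450 come from section 9, Study end-point. The four tissue types come from section 5. No alpha, power, effect size or standard deviation is given, so 150 and 300 cannot be reproduced by a sample-size formula. Only capacity can be checked.

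**Is 10,000 cells per sample or in total?** The text does not say. As a total, the reads needed are 10,000 × 20,000 = 2.0 × 10⁸, which is 2.0 × 10⁸ / 3.3 × 10⁹ = 6.1% of the flow cell. Per sample is the more plausible reading and is assumed below.

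**Capacity of one flow cell.**
- 3.3 × 10⁹ / 2.0 × 10⁸ = 16.5, so 16 whole samples.
- If only 70% to 90% of reads are usable (an assumed range), 11 to 14 samples.
- 16 / 450 = 3.6%.
- Equal split over four tissue types: 16 / 4 = 4 each. If neurospheres are sequenced for each type as well: 16 / 8 = 2 each. The protocol states no split.

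**If every specimen were sequenced.**
- 450 × 2.0 × 10⁸ = 9.0 × 10¹⁰ reads, or 27.3 flow cells: at least 28, and 29 at 16 whole samples each (450 / 16 = 28.1).
- On one flow cell, depth would be 3.3 × 10⁹ / (450 × 10,000) = 733 reads per cell.
- If each Hirschsprung's specimen gave three regions, there would be 150 × 3 + 300 = 750 samples: 45.5 flow cells (at least 46), or 440 reads per cell on one.

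These results show that sequencing every specimen is not what the section describes. They do not show that the protocol asks for it.

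**What 4 per type could show (scale only).** The protocol chooses none of these methods.
- The 95% interval half-width for a mean is t(0.975, 3) / √4 = 1.59 between-child standard deviations.
- With a two-sided 5% t-test and 80% power, 4 v 4 detects about 2.38 standard deviations.
- An exact permutation test at 4 v 4 cannot give a two-sided p-value below 2/70 = 0.029. A t-test has no such floor.

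**Reading the sections together.** Section 9 gives a sum over outcomes. The handling section allows each assay a subset. The sequencing sentence describes storing samples and then processing them as a batch. So about 16 sequenced samples and 450 specimens, shared among culture, histology, qPCR, cytometry, stimulation and transplantation, fit together.

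**Follow-up.** The qPCR section already plans to confirm sequencing findings, adds RNAscope for location and names six markers in advance. Cell sorting adds flow cytometry. The stimulation section fixes three pathways before any sequencing result. Sequencing adds to these lists and does not replace them. As an illustration, three regions from each of 4 Hirschsprung's children plus 4 controls fill 16 places (12 + 4). That uses 16 specimens if a specimen is one region, or 8 if it is a resection, leaving 434 or 442 of the 450. Confirmation in children who were not sequenced is therefore possible as things stand.

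**The case for a change.** The best case for a change is that allowing a subset does not say how large it is. The only figures that bound it are the sequencing ones, and they imply 16 or fewer on a single run. Four children per tissue type is thin for a search described in terms of significant differences. How many children are sequenced is also a tissue-allocation choice, which has to be made before the run. Stating the number, and defining specimen, would cost only words.

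Part of this stands. The number sequenced and the unit are not written down, and 4 per type would separate only very large differences from variation between children.

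The rest is inference. A limit of 16 needs 10,000 cells per sample and only one flow cell; four per type also needs an equal split. The protocol states none of these and does not exclude a second run. The sequencing parameters are worded as estimates, and the first milestone is still to optimise the sequencing method. The second milestone is identification and description, for which the protocol sets no error rate or power, so weak power for a test it does not specify is not a shortfall against the plan.

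Nor is there a clear gain from the obvious alternative. Halving the depth, 3.3 × 10⁹ / (10,000 × 10,000), or halving the cells, 3.3 × 10⁹ / (5,000 × 20,000), gives 33 samples, about 8 per type. That buys more children at the price of resolution in the progenitor cells the study wants to find. It is a trade-off best settled during optimisation.

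**Conclusion.** No change follows. The capacity figure is right: about 16 samples on one S2 flow cell, or 3.6% of 450, if 10,000 cells is per sample and all reads are usable. The contradiction is not there, because the 450 covers all outcomes and the protocol lets each investigation use a selection of tissues. The figure of 4 per tissue type rests on two further assumptions, a single run and an equal split.

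What remains is missing detail: how many samples will be sequenced, in how many runs, and what counts as a specimen. A competent team would settle these when selecting samples for the run. A discovery set of this size, with the confirmation already planned, is a reasonable way to reach the descriptive milestone. This judgement assumes that the children, not the cells, are treated as the independent units. The protocol's Statistical analysis section leaves methods open and provides for consulting biostatisticians, and nothing in it points the other way.

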## 11. Dissemination

The results will be widely disseminated by presentations at national and international gastroenterology, paediatric surgical and developmental biology meetings, and by peer-reviewed publication in appropriate gastroenterology or developmental biology journals. The research group hold regular patient and family meetings where research findings are fed back to participating families. The group's close links with Hirschsprung's charities, particularly CHAMPS, means that research finds are also fed back through the group's channels.

